Vitamin D, in addition to its role in calcium and bone homeostasis, is a multifunctional regulator of both innate and adaptive immune responses.⁷⁻¹¹ The scientific premise of the proposed clinical trial is that circulating concentrations of vitamin D₃, the parent compound, are the principal determinant of the anti-infective and immunomodulatory effects of supplementation.¹²⁻¹⁴ With *monthly bolus* oral vitamin D₃, the parent compound is cleared from the circulation within days.^{7, 12, 13, 15, 16} In our earlier clinical trial *monthly bolus* oral vitamin D₃, neither the standard- nor high-dose treatments would produce sustained increases in circulating vitamin D₃, potentially explaining the uniformity of response to the two treatments. Apparently, a year of treatment with bolus dosing was needed to permit sufficient amounts of vitamin D₃ to accumulate within cells of the immune system and produce the observed reductions in the rates of respiratory events. Our hypothesis is that **daily oral vitamin D₃** will rapidly reduce the rate of respiratory complications during Year 1. We propose a 2-year controlled, double-blind, randomized Phase 2 clinical trial comparing the efficacy in reducing the rate of respiratory events in sickle-cell disease of **daily oral vitamin D₃ (3,333 IU/d)** with **monthly bolus oral vitamin D₃, (100,000 IU/mo)** as a control. Baseline concentrations of 25-hydroxyvitamin D in our population (mean ~14 ng/mL) guide the choice of the high-dose daily treatment for the proposed trial and are too low to permit inclusion of a placebo control.

This Phase 2 clinical trial, designed to be a minimal risk study, has three specific aims:

- (1) to determine whether **daily oral vitamin D₃ (3,333 IU/d)** given to children and adolescents with sickle-cell disease, compared to **monthly bolus oral vitamin D₃, (100,000 IU/mo)** will more rapidly reduce the rate of respiratory events, defined as respiratory infections, exacerbations of asthma, and episodes of the acute chest syndrome;
- (2) to evaluate the effects of **daily oral vitamin D₃** on pulmonary function; and
- (3) to examine the effects of **monthly oral vitamin D₃** on immune function, using measures of T-cell effector and regulatory function and of systemic inflammation.

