Prior to initiation of treatment, subjects will have baseline assessments that will include: (i) pulmonary function test (limited to age above 5y/o); and (ii) blood tests for biomarkers of inflammation (complete blood count, C-reactive protein, and Th1/Th2 cytokines). Participants will be seen monthly in person or remotely in a telehealth visit for confirmation of administration of study drug, accounting of unused study drug, interval history including respiratory events and adverse event monitoring. Laboratory safety assessments will include serum albumin-corrected calcium and spot urinary calcium-creatinine ratios to be obtained immediately before study drug administration, and performed at intervals as shown in the Table (Schedule of Study Evaluations) to monitor hypercalcemia and hypercalcuria. Abnormal laboratory values will be reviewed by the Clinical Trial Safety Officer to determine clinical significance and need for intervention, as described in detail below.

Daily vitamin D for prevention of respiratory complications in sickle cell disease

[figure not shown]

Figure: Profile of the Phase 2 ViDAS-2 clinical trial design.

Blood specimens for 25(OH)D and vitamin D₃ will be collected every third month for the first six months, then at months 6, 12, 18 and 24, stored at -112°F (-80°C) freezer, and analyzed in a single batch at the end of the study by Ultra Performance Liquid Chromatography-Tandem Mass Spectrometry (See *below* for Vitamin D assay). Adverse events will be determined according to the Common Terminology Criteria of Adverse Events version 4.0. Pulmonary function tests will be repeated at 12-months and 24-months after initiation of treatment, while the biomarkers of inflammation, the health-related quality of life questionnaire and the Block Calcium and Vitamin D screener and sun exposure questionnaires will be collected every 6 months. Table 3 below outlines the schedule of study evaluations.

Primary Outcome Measure: Respiratory Events

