Our primary study analysis will examine the annual rate of respiratory events (the sum of respiratory infections, asthma exacerbations and episodes of acute chest syndrome) in children with sickle cell disease randomized in a double-blind manner to the daily and monthly doses of oral vitamin D₃. The primary statistical analysis will be by "intention to treat" and will use a semiparametric regression method to estimate the between group difference in intensity (events per subject per unit of time at risk) with the assumption that covariates have a multiplicative effect on the mean and rate functions. This approach takes account of the skewed distribution of the respiratory events. The results of this analysis will be summarized as a regression parameter estimate, with the standard error of the estimate, a chi-square test with associated p-value, and a hazard ratio with confidence limits expressing the rate difference of the daily relative to the monthly group (as described in Lin, DY, Wei, LJ, Yang, I, and Ying, Z. "Semiparametric regression for the mean and rate functions of recurrent events," *J R Stat Soc Series B Stat Methodol*, 2000; 62:711–730).⁶³ This approach can adjust for group differences in time-independent covariates and estimate rate ratios at specific values of covariates and at specific times of follow up. The annualized rate of events and the average inter-event interval (in two-week intervals, the observation protocol) will be entered as time-independent covariates. After testing the initial hypothesis of overall group difference, we will sequentially test the between-treatment group differences in the study design enrollment criteria strata: age, gender and therapy (hydroxyurea). Secondary analyses using the same statistical framework will separately test the study hypotheses at the one-year time point. The functional form of covariates and proportional hazards assumptions will be checked for all models and cumulative hazard plots and cumulative residual plots will be used to display group differences in the evolution of events and model fit, respectively.

Subsidiary analyses will be made to examine a number of secondary study hypotheses with respect to the effects of vitamin D₃ on changes in pulmonary function and airway inflammation, and on immune system, but these comparisons have not entered into the sample size calculation. Data will be summarized as means \pm standard

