deviation or as counts and proportions. Study Group differences in continuous measures at baseline will be compared using independent *t* tests and differences in dichotomous categorical measures at baseline will be compared using Fisher's exact test.

Sample size

For sample size estimation, we base our estimate of the annual rate of respiratory events on the rate observed in the earlier ViDAS-1 trial in our study population, a mean annual baseline respiratory event rate of 4.1. For our estimate of the treatment effect, we use the observed reduction in annual mean respiratory event rate in the earlier ViDAS-1 trial for *monthly* bolus oral vitamin D3, 100,000 IU/mo (2.5 mg/mo), from Treatment Year 1 to Treatment Year 2 from 4.28 ± 0.36 (SEM) to 1.49 ± 0.37 , or a decrease of about 65 percent. Using a conservative estimate of a treatment effect of 50 percent reduction in the rate of respiratory events as the minimal *clinically* significant difference to be detected, **26 subjects in each group will be sufficient to detect an effect size of this magnitude with a two-sided significance level of alpha = 0.025 and 90 percent power. Allowing for as much as a 15 percent loss of participants during the two-year study (due to clinical events, such as initiating chronic red blood cell transfusion therapy, failure of compliance or exclusion or withdrawal for any reason), then our sample size estimate is $26/0.85 = 31$ participants in each treatment group, or a total of 62 participants.** Although the secondary analyses planned have not entered into the calculation of the sample size required for the proposed study, the conservative specification for the treatment effect; 90 percent power; and a generous allowance for loss of participants, should help provide adequate power for subsidiary comparisons.

Annualized Event Rate and Inter-Event-Interval (IEI)

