All primary and secondary outcome analyses will be performed under the intent-to-treat principle. Crude estimates of group differences in the annualized event rate and average inter-event-interval during Treatment Year 1 and Treatment Year 2 will be analyzed by linear mixed models for repeated measures with fixed effects for group, time and group-by-time interaction, and an AR(1) covariance structure. Analyses of secondary outcomes for pulmonary function testing will also use this approach. Further analysis of treatment group differences will be assessed using a variation of the Cox Proportional Hazards model with a counting process input of start and stop times for each event and the robust sandwich covariance estimator of Lin.⁶³ This approach models hazard for recurrence under the assumption of proportional mean processes and generates hazard ratios with 95% confidence intervals and Wald Chi-Square statistics for testing the null hypothesis. We will evaluate the influence of the event rate, average IEI as covariates and calculate between treatment group hazard ratios. We will also evaluate the influence of randomization stratifying variables as covariates of the estimate of the between treatment group difference: sex (female vs male), age (child vs adolescent) and hydroxyurea use (use vs non-use). For participants in each treatment group who withdraw from the study prior to completion of the protocol, we will repeat the primary intent-to-treat analysis with the subset of participants who completed the two-year study in a "per protocol" analysis. Finally, treatment group differences in adverse events of least grade 2 severity will be assessed with chi-square or Fisher's Exact test. We will only present comparisons of events where three or more instances are reported over the two-year treatment period.

DATA AND SAFETY MONITORING

Adherence to protocol: Conduct of the clinical trial will be in accordance with this new protocol for the ViDAS-2 study in our Investigational New Drug application. This protocol includes the appointment of a Clinical Trial Safety Officer to review laboratory results as they become available, and the formation of a Data and Safety Monitoring

Board (DSMB) consisting of an expert in pediatric sickle cell disease, a biostatistician, and a Pediatric Endocrinologist with expertise in vitamin D metabolism. The DSMB will meet bi-annually.

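### Pulmonary function (Aim 2): the mixed model names no baseline term although a baseline test is collected, and AR(1) over three visits could misstate standard errors of change in either direction

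*Combined protocol and SAP*

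**What the plan says.** The SAP's Treatment Outcome Analysis section specifies a mixed model for the annualized event rate and the inter-event interval in Treatment Years 1 and 2, with "fixed effects for group, time and group-by-time interaction, and an AR(1) covariance structure". It then adds: "Analyses of secondary outcomes for pulmonary function testing will also use this approach". No baseline term is listed. The covariates named elsewhere in the SAP (event rate, inter-event interval, age, sex, hydroxyurea) belong to the recurrent-event model. The t tests of baseline measures compare the groups but adjust nothing.

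Section 6a (Study protocol) lists a "pulmonary function test (limited to age above 5y/o" among the assessments before treatment, and says: "Pulmonary function tests will be repeated at 12-months and 24-months after initiation of treatment". That makes three visits. The count rests on this text alone: the schedule table, as extracted, shows only two pulmonary function marks, but it may be broken and is not relied on here.

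The SAP describes the target as "changes in pulmonary function and airway inflammation, and on immune system", and says of these comparisons, "but these comparisons have not entered into the sample size calculation".

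**The concern.** The model was written for two outcomes whose stated times are both after randomization, and was then carried over to an outcome that also has a pre-treatment value. An analyst could fit at least three models from this text: baseline as a level of time, baseline as a covariate, or baseline ignored. They give different contrasts and standard errors. The reference to changes in pulmonary function makes baseline as a level of time the more natural reading. The restriction of the parent sentence to Treatment Years 1 and 2 leaves doubt.

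Two separate things are at stake.

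- **Precision.** Aim 2 was not sized, so precision is its main constraint, and the baseline value is already being collected.
- **Correct standard errors.** If baseline is one of three responses, AR(1) imposes a particular decay of correlation. If the true decay differs, the reported standard error of a change from baseline is wrong.

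**Working it through.** **Inputs.** The Sample size section gives 26 completers per arm. That figure reproduces for the primary outcome as a comparison of two means: SD = 0.37 × √31 = 2.06, difference 50% of 4.1 = 2.05, two-sided alpha 0.025, power 90%, so n = 2 × 12.41 × 2.06² / 2.05² = 25.1, rounded up to 26; then 26/0.85 = 30.6, rounded up to 31. The documents give no figure for pulmonary function. Assumed here: within-child correlation ρ of 0.6 to 0.9, equal variances across visits, complete data.

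**1. Precision from baseline adjustment** (units of one SD, n = 26 per arm, variance of the group difference at one follow-up visit)

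- Follow-up only: 2/n
- Change from baseline: 2 × 2(1 − ρ)/n
- Baseline-adjusted: 2(1 − ρ²)/n × (1 + 1/48), the last factor being the cost of estimating the slope

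The adjusted-to-change ratio is (1 + ρ)/2 × 49/48. The adjusted-to-follow-up ratio is (1 − ρ²) × 49/48.

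| ρ | adjusted / change | adjusted / follow-up only |
|---|---|---|
| 0.6 | 0.82 | 0.65 |
| 0.7 | 0.87 | 0.52 |
| 0.8 | 0.92 | 0.37 |
| 0.9 | 0.97 | 0.19 |

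Variance is therefore 3 to 18% lower than for change, or 35 to 81% lower than for follow-up only. The gain over change vanishes at ρ = 2 × 48/49 − 1 = 0.959.

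**2. Standard error under AR(1), all three tests as responses.** With equal variances, the AR(1) likelihood depends on the true correlations only through the sum of the two adjacent ones (0-12 and 12-24). The fitted r is their average, and the fitted 0-24 correlation is r². For change from baseline, reported over true standard error is

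- month 24: √[(1 − r²)/(1 − ρ₀₂₄)]
- month 12: √[(1 − r)/(1 − ρ₀₁₂)]

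| true correlations 0-12 / 12-24 / 0-24 | r | month-24 ratio | month-12 ratio |
|---|---|---|---|
| constant 0.6 | 0.60 | 1.26 | 1.00 |
| constant 0.7 | 0.70 | 1.30 | 1.00 |
| constant 0.8 | 0.80 | 1.34 | 1.00 |
| constant 0.9 | 0.90 | 1.38 | 1.00 |
| 0.80 / 0.80 / 0.70 | 0.80 | √(0.36/0.30) = 1.10 | 1.00 |
| 0.80 / 0.80 / 0.64 (true AR(1)) | 0.80 | 1.00 | 1.00 |
| 0.80 / 0.80 / 0.55 | 0.80 | √(0.36/0.45) = 0.89 | 1.00 |
| 0.70 / 0.85 / 0.65 | 0.775 | √(0.399/0.35) = 1.07 | √(0.225/0.30) = 0.87 |

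At constant correlation the month-24 ratio reduces to √(1 + ρ), which gives the 27 to 38% excess (1.265 to 1.378). Simulated trials of 26 per arm, fitted by REML, agree. A nominal 5% test of the month-24 change rejects about 1% of the time at constant correlation and about 8% at 0.80/0.55. The month-12 test rejects about 9% of the time in the last row.

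**3. Baseline as a covariate.** Only months 12 and 24 are then responses. They have one correlation between them, so AR(1) imposes no decay and part 2 does not arise.

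**The case against.** The strongest reply is that this is refinement and not a defect. On the more natural reading, adjustment saves only 8% of variance at correlation 0.8 and 3% at 0.9. The AR(1) error needs baseline to be a response and the test to be a change from baseline, and the plan names no such contrast. A plain month-24 difference with complete data has the right standard error under AR(1). The joint group-by-time test is near its nominal size in simulation (about 4 to 6% at constant correlation). All the correlations are assumed. This stands, and it is why the point is small. It does not remove the open choice, which can be closed at almost no cost.

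Three stronger readings are tempting, and the documents do not support them.

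- **Adding the two effects.** The 35 to 81% saving needs baseline to be unused. The AR(1) error needs baseline to be a response. Both cannot hold at once.
- **Treating the AR(1) error as only conservative, and month 12 as safe.** The first is true only if the 0-24 correlation is at least the square of the fitted adjacent one. The second holds only if the 0-12 correlation is no lower than the 12-24 one; they agree exactly only when the two are equal. The documents give no correlations that would settle either. Month 12 may well be of interest, since the trial's hypothesis is that daily dosing "will rapidly reduce the rate of respiratory complications during Year 1".
- **Counting unstructured covariance as a gain in precision.** For the three-visit change contrast with complete data, it corrects the standard error and leaves the estimate unchanged. Even with the plan's 15% loss, placed by assumption as 26 complete, 3 with baseline and month 12 only, and 2 with baseline only per arm, the right covariance lowers the month-24 variance by at most about 2.5% in the patterns examined.

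**Conclusion.** The concern holds in a limited form. The plan does not say how the baseline pulmonary function test enters the model, and adjusting for it is a nearly free improvement. At assumed correlations of 0.6 to 0.9 with 26 per arm, variance falls by about 3 to 18% or by about 35 to 81%, depending on which reading would otherwise apply.

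The AR(1) point is conditional on a three-visit response model and a change-from-baseline contrast. Under equal variances, the month-24 standard error runs from about 38% too large to about 11% too small over the patterns shown. The month-12 standard error is about 13% too small in one of them. A pattern outside this set could fall outside that range.

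A reader might infer that the trial's main result is at risk. It is not: the primary analysis is a recurrent-event model for respiratory events, and pulmonary function is a secondary aim outside the sample size calculation. Confidence is moderate, because the size of both effects rests on correlations that the documents do not give.

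**What to change.** In Treatment Outcome Analysis, add one or two sentences for pulmonary function that choose between:

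- **(a)** months 12 and 24 as responses, with group, time, group-by-time, baseline value and baseline-by-time; or
- **(b)** all three visits as responses, with a common baseline mean across groups and an unstructured covariance.

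Name the contrast and visit to be tested.

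In (b) the unstructured covariance matters. Keeping AR(1) there would give a reported month-24 standard error about 17 to 35% above the one under the right covariance at constant correlation 0.6 to 0.9. In (a) it only relaxes the assumption of equal variances.

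**Cost.** Programming, and four more covariance parameters than AR(1) in (b) (six against two) or one more in (a) (three against two). Option (a) also drops children with no baseline test. If ages follow the earlier trial (mean 9.9, SD 3.9, taken as normal and truncated to 3 to 21), that is about 7% if the limit means age 5 or over and about 13% if it means age 6 or over. Option (b) can use some of them, but only if they are tested once old enough. The protocol does not say, so the added text should.

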The results of our clinical trial could offer a simple and low-cost intervention to help avert serious respiratory complications in sickle-cell disease that could lead to important reductions in morbidity and death in children with sickling disorders and to major changes in the management of their vitamin D status.

4. General investigational plan

Acute respiratory illness is a principal cause of morbidity and mortality worldwide¹⁷ and can be devastating for children with sickle cell disease, an inherited red blood cell disorder affecting an estimated 100,000 Americans,³ predominantly of African ancestry. Sickle cell disease is characterized by a shortened life expectancy, hemolytic anemia, acute episodes of vaso-occlusive pain, and recurrent, chronic damage to vital organs.^{3, 4} Pulmonary manifestations are common and often severe. Respiratory infections or asthma attacks that would have no lasting effects in individuals with no sickle hemoglobinopathy can trigger severe or even fatal manifestations in those with sickle cell disease.¹⁸ For instance, children with influenza and sickle cell disease are hospitalized at a rate more than 50-fold greater than children without sickle cell disease.¹⁹ Asthma is common, affecting 15 to 28% of children with sickling disorders.⁵ Unique to sickle cell disease is a respiratory complication characterized by fever, respiratory symptoms and a new pulmonary infiltrate, known as "acute chest syndrome."⁶ Commonly precipitated by respiratory infections and asthma, the acute chest syndrome is the leading cause of death in sickle cell disease.^{5, 6} The pathogenesis of sickle cell lung disease is unclear, but involves microvascular occlusion, hemolysis-induced endothelial dysfunction and vasculopathy that produce a chronic inflammatory state, often exacerbated by an infectious trigger.^{3, 20, 21} Compromised immunity from functional asplenia may contribute to the risks of respiratory infections and pulmonary disease.²² Improved vaccination and penicillin prophylaxis have greatly reduced the risk of bacterial pathogens but are ineffective against viruses and atypical organisms that now predominate as risks for acute chest syndrome.²³

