Vitamin D, in addition to its role in calcium and bone homeostasis, is a multifunctional regulator of innate and adaptive immune responses and of inflammation.⁷⁻¹¹ Vitamin D acts, in part, through its metabolite, 1,25-dihydroxyvitamin D (1,25(OH)₂D),^{24, 25} which binds to the vitamin D receptor to function as a transcription factor inducing vitamin D responsive genes that are present in most if not all cells of the immune system.²⁶ 1,25(OH)₂D mediates the innate immune host response against respiratory tract pathogens by stimulating expression of cathelicidin (hCAP18/LL37), an antimicrobial peptide with activity against viral, bacterial and fungal pathogens.^{27, 28} 1,25(OH)₂D regulates the adaptive immune system by modulating T-lymphocyte proliferation and function, and by down-regulating the inflammatory response and cytokine expression.²⁹ In addition to these functions of 1,25(OH)₂D, the parent compound vitamin D itself is a potent and general mediator of endothelial stability and barrier function.³⁰ A recent Cochrane review of randomized clinical trials identified high quality evidence that vitamin D supplementation reduced the risk of asthma exacerbations, although too few pediatric trials were included to permit definitive conclusions for children.^{31, 32} While observational studies consistently have found significant associations between low vitamin D levels and increased susceptibility to respiratory infections, randomized clinical trials examining the effects of vitamin D supplementation on the risk of respiratory infections have had conflicting findings due, in part, to differences in the baseline status of the participants, the duration of the studies and the amount and frequency of dosing.³³⁻³⁶

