Children with sickle cell disease are at high risk for vitamin D deficiency due to limited sun exposure, dark skin color and poor nutrition. Our own and other observational studies have found that most children with sickle cell disease have low vitamin D status.^{37, 38} Contrary to an earlier hypothesis,³⁹ the low levels of vitamin D in black Americans are not explained by differences in the concentration of vitamin D-binding protein.^{40, 41} Considering that individuals with low vitamin D levels seem to derive the most benefit from supplementation³⁶ and that children with sickle cell disease have a heightened susceptibility to respiratory infections and asthma together with a greatly increased vulnerability to complications, we conducted the ViDAS-1 study, a 2-year active-controlled, double-blind, randomized clinical trial comparing high-dose oral vitamin D₃, 100,000 IU, given once a month under observation (daily equivalent 3,333 IU/day), with standard-dose oral vitamin D₃, 12,000 IU, given once a month under observation (daily equivalent 400 IU/day),⁴² to determine if oral vitamin D₃ (cholecalciferol) can reduce the risk of respiratory complications in children and adolescents, 3 to 20 years old, with sickle cell disease (ViDAS-1 study). Because of the established risks of inadequate mineralization of the skeleton associated with vitamin D deficiency,^{9, 42-44} a placebo group could not be included in the study design.

The ViDAS-1 trial results have been presented in our annual reports and are summarized here to clarify the rationale for the ViDAS-2 trial. Seventy sickle cell subjects, ages 3-20 years, with baseline records of respiratory events over one year before randomization, underwent screening. Sixty-two subjects with 25-hydroxyvitamin D levels 5-60 ng/mL were randomly assigned in a 1:1 ratio to oral vitamin D₃ 100,000 IU (n=31) or 12,000 IU (n=31), under observed administration once monthly for two years. The primary outcome was the annual rate of respiratory events (respiratory infection, asthma exacerbation, acute chest syndrome) ascertained by use of a

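### Asthma history and screening 25(OH)D, both linked by the protocol to respiratory events, enter no efficacy model: a missed gain in efficiency and prespecification, not a validity error

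*Combined protocol and SAP*

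**What the plan says.** In the Statistical Analysis Plan, the paragraph on the primary analysis specifies a semiparametric recurrent-event model. It enters the annualized event rate and the average inter-event interval (IEI) as covariates, then plans to "sequentially test the between-treatment group differences in the study design enrollment criteria strata: age, gender and therapy (hydroxyurea". Treatment Outcome Analysis repeats the same set: event rate, IEI, and "sex (female vs male), age (child vs adolescent) and hydroxyurea use (use vs non-use". The mixed model for crude estimates has only group, time and their interaction. The primary-analysis paragraph adds that the method is able to adjust for time-independent covariates, without naming others.

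Section 4 (General investigational plan) says "Asthma is common, affecting 15 to 28% of children with sickling disorders" and names asthma as a trigger of acute chest syndrome. It also says that "observational studies consistently have found significant associations between low vitamin D levels and increased susceptibility to respiratory infections" and that "individuals with low vitamin D levels seem to derive the most benefit from supplementation". Under Primary Outcome Measure, asthma exacerbation is one of three endpoint components, and wheezing and difficulty breathing are qualifying symptoms.

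Section 6a measures 25(OH)D in every child at screening and uses it for eligibility. For asthma, the only screening source is an unspecified medical history.

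**The concern.** The named covariates leave the model without a defined baseline measure of respiratory risk. The section on Annualized Event Rate and Inter-Event-Interval defines the event rate over Treatment Years 1 and 2, so it is measured after randomisation. It gives no baseline-period rate. The screening and randomisation questionnaires look back only two weeks.

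Two things are at stake. The first is precision: with about 31 children per arm and no balancing on asthma, unexplained variation between children widens the interval, and a chance imbalance can move the estimate in the trial as realised. The second is prespecification. The SAP compares baseline characteristics by significance tests and notes that the model can adjust for group differences, without saying for which variables. That leaves room to choose covariates after seeing the data.

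**Working it through.** **1. The plan's own figure.** Inputs from the Sample size section: "a mean annual baseline respiratory event rate of 4.1"; "a treatment effect of 50 percent reduction in the rate of respiratory events", so a difference of 4.1 × 0.5 = 2.05; "with a two-sided significance level of alpha = 0.025 and 90 percent power". The SD is not stated. I derive it from the ViDAS-1 SEM of 0.37 with 31 per arm: 0.37 × √31 = 2.06.

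n = 2(2.241 + 1.282)² × 2.06² / 2.05² = 25.1, so 26 per group. Then 26/0.85 = 30.6, so 31 per group and 62 in total. The figure reproduces.

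**2. Gain for a given explained variance.** Multiply n by (1 − R²):

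| Assumed R² | n per group | Power at 26 per group |
|---|---|---|
| 0 | 26 | 91.1% |
| 0.05 | 24 | 92.5% |
| 0.10 | 23 | 93.8% |
| 0.15 | 22 | 95.1% |
| 0.25 | 19 | 97.1% |

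**3. What asthma could explain.** R² = p(1 − p)[μ₀(RR − 1)]² / SD², with μ₀ = 4.1/[1 + p(RR − 1)]. The prevalence p is from section 4; the asthma rate ratio RR is assumed.
- p = 0.15, RR = 1.25: μ₀ = 3.95, R² = 0.124/4.24 = 0.03.
- p = 0.28, RR = 1.5: μ₀ = 3.60, R² = 0.652/4.24 = 0.15.

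**4. How much variation there is to explain.** The six ViDAS-1 annual rates average 3.15. Their SEMs imply a mean variance of 4.06. Dispersion is (4.06 − 3.15)/11.37 = 0.08, where 11.37 is the mean squared rate. The between-child share of the log-rate-ratio variance over one year is then 0.16/(1/4.1 + 1/2.05 + 0.16) = 18%, and over two years 30%. This caps the gain from all baseline covariates together. The SEMs are nearly constant (0.35 to 0.37) while the rates run from 1.49 to 4.34, which suggests pooled standard errors, so the true dispersion could be larger.

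**5. Simulated power.** Log-linear rate model with robust standard errors, 26 per arm, one year, two-sided 0.025, at least 1,500 trials per row. Where 25(OH)D is included, its assumed log-rate slope is 0.1 to 0.2 per 10 ng/mL.

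| Asthma RR (assumed) | Prevalence | Residual dispersion | True ratio | Terms added | Without | With | Change (points) |
|---|---|---|---|---|---|---|---|
| 1.25 | 15% | 0.08 | 0.50 | both | 93.7% | 93.2% | −0.5 |
| 1.5 | 28% | 0.08 | 0.50 | both | 92.1% | 92.9% | +0.8 |
| 1.5 | 28% | 0.2 | 0.50 | both | 84.0% | 86.9% | +2.9 |
| 1.5 | 20% | 0.104 | 0.50 | asthma | 90.9% | 92.0% | +1.1 |
| 1.5 | 20% | 0.104 | 0.60 | asthma | 70.9% | 72.9% | +2.0 |
| 2 | 28% | 0.2 | 0.50 | both | 76.5% | 84.9% | +8.4 |
| 2 | 28% | 0.5 | 0.50 | both | 60.9% | 66.2% | +5.3 |
| 2 | 20% | 0.026 | 0.50 | asthma | 91.0% | 96.5% | +5.5 |
| 2 | 20% | 0.026 | 0.60 | asthma | 72.7% | 83.7% | +11.0 |

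Each power figure near 90% has a Monte Carlo standard error of up to √(0.9 × 0.1/1500) = 0.8 points. Type I error was similar with and without the added terms. Adding 25(OH)D when it predicts nothing cost 0.5 to 0.8 points.

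**6. Chance imbalance.** By exact binomial calculation at 31 per arm, the arms differ by four or more children with asthma in 21% (prevalence 15%) to 32% (28%) of randomisations. An 8 v 4 split shifts the rate ratio by (1 + 8/31)/(1 + 4/31) = 1.11 if asthma doubles the rate, and by 35/33 = 1.06 if the ratio is 1.5.

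**7. Effect of the post-randomisation covariates.** With the on-treatment event count in the model and a true ratio of 0.50, simulated power is about 6 to 10%. Adding asthma and 25(OH)D leaves it at 7 to 8%.

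**8. Interaction with 25(OH)D.** In ViDAS-1, 77% were below 20 ng/mL. Of 26 per arm, about 20 and 6 fall on either side. SE = √[0.892 × (1/20 + 1/6)] = 0.44, so the ratio of rate ratios detectable with 80% power at 0.05 is exp(−2.80 × 0.44) = 0.29 over one year. Over two years it is 0.39.

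**The case against.** The strongest case is that nothing here is an error. Randomisation makes the comparison valid without these covariates, and the standard error already allows for chance imbalance. The 11% shift in step 6 is 0.108/0.197 = 0.55 of a standard error. Adjusting for stratification factors is conventional. All of this stands, so a reader who infers that the omission biases the result goes too far.

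The gain may also be slight. The RR 2 rows with dispersion 0.026 are the favourable end: asthma alone would contribute 0.16/1.44 = 0.111 to dispersion, about 80% of the total and more than the 0.08 that ViDAS-1 implies. Infection followed by an asthma exacerbation counts as one event, and children whose pulmonary medication changed recently are excluded. Both weaken asthma as a predictor. ViDAS-1 baseline 25(OH)D ran only from 5 to 28 ng/mL. These points stand as limits on size, but no document figure settles the asthma rate ratio either way.

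A reader might also infer that the protocol expects baseline 25(OH)D to modify this trial's treatment effect. The documents do not support that. The sentence in section 4 is about supplementation in general. Both arms here receive about the same monthly amount, and the stated premise is circulating parent vitamin D₃. The monthly arm is described as a stand-in for placebo, which makes the question reasonable to explore but does not state the modification.

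Finally, asthma is not a listed screening item, so it cannot be said that both variables are already collected.

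**Conclusion.** The point holds as one of efficiency and prespecification. Two characteristics that the protocol links to respiratory events are absent from every efficacy model, and 25(OH)D is already measured in every child. The expected gain is about 0 to 3 power points at asthma rate ratios of 1.25 to 1.5, and about 5 to 11 at 2. These ratios, the 25(OH)D slopes and the residual dispersions are assumptions. The cost if a covariate is not prognostic is about one point or less. The gain also depends on removing covariates measured after randomisation: while the treatment-phase event rate and IEI stay in the model, step 7 shows nothing is recovered. The trial could not establish effect modification by 25(OH)D, so that belongs in a descriptive report only.

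**What to change.** In the primary-analysis paragraph of the SAP and in Treatment Outcome Analysis:

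- Name the covariates of the recurrent-event model as sex, age group, hydroxyurea use, screening 25(OH)D (continuous) and physician-diagnosed asthma (yes/no).
- Exclude from that model any covariate measured after randomisation, including the treatment-phase event rate and IEI.
- Add asthma as a defined yes/no item in the screening medical history, recorded before randomisation. For any child already randomised, take it from pre-randomisation records, blind to allocation.
- If a treatment-by-25(OH)D interaction is reported, label it exploratory, keep 25(OH)D continuous, and give an estimate with interval and no success criterion.

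The cost is SAP wording and one case-report field; no new assays, visits or participants. At the design rates, one year yields about 26 × (4.1 + 2.05) = 160 events, which can carry treatment plus five covariates. With a log link and randomised treatment, the rate ratio keeps its meaning after adjustment.
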